## Diagnosis and main criteria for exclusion:

#### **Exclusion criteria for all patients**

#### Medical Conditions

- 1. Patients with uncontrolled intercurrent illness, including but not limited to:
  - a. Ongoing or active infection which requires systemic treatment with antibiotics or corticosteroid therapy within 14 days before the first dose of IMP.
  - Symptomatic congestive heart failure (Grade III or IV as classified by the New York Heart Association), myocardial infarction within 3 months before screening, unstable angina pectoris, or cardiac arrhythmia.
  - c. Known recent history (in the past 5 years) or presence of significant pulmonary conditions such as uncontrolled chronic lung disease, or any evidence of interstitial lung disease, or active, non-infectious pneumonitis.
  - d. Uncontrolled hypertension defined as systolic blood pressure ≥160 mmHg and/or diastolic blood pressure ≥100 mmHg, despite optimal medical management.

CONFIDENTIAL Page 18 of 122

- e. Known primary immunodeficiencies, either cellular (e.g., DiGeorge syndrome, T cell negative severe combined immunodeficiency [SCID]) or combined T- and B-cell immunodeficiencies (e.g., T- and B-cell negative SCID, Wiskott Aldrich syndrome, ataxia telangiectasia, common variable immunodeficiency).
- f. Ongoing or recent evidence (within the past year) of significant autoimmune disease that required treatment with systemic immunosuppressive treatments which may suggest risk for immunerelated adverse events (AE).

Note: Patients with autoimmune-related hyperthyroidism, autoimmune-related hypothyroidism who are in remission, or on a stable dose of thyroid-replacement hormone, vitiligo, or psoriasis may be included.

- g. Non-healing wound, skin ulcer (of any grade), or bone fracture.
- h. Patients with prior allogeneic stem cell or solid organ transplantation.
- i. Patients with the following risk factors for bowel perforation (e.g., history of acute diverticulitis or intra-abdominal abscess in the last 3 years; history of gastrointestinal obstruction or abdominal carcinomatosis).
- j. Patients with uncontrolled type 1 diabetes mellitus.

  Note: Patients controlled on a stable insulin regimen are eligible.
- k. Patients with uncontrolled adrenal insufficiency.

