- For details on safety laboratory tests, see Section 10.2. If the time interval between screening laboratory tests and C1D1 (baseline) is more than 7 days, tests must be repeated at C1D1. Screening serum creatinine will be used to calculate patient's glomerular filtration rate required for inclusion criterion. If warranted by dipstick results, urine sediment will be microscopically examined. Serology can be done at earlier screening time point.
- [12] At treatment visits, patients will also be monitored for TEAEs for at least 4 to 6 h post-treatment.
- [13] For details on DLT assessment period and DLT criteria, see Sections 6.6.1.2 and 6.6.1.1.
- [14] For details on patient's survival status and disease status, see Sections 10.9 and 8.1.
- Blood collection before and 4 h ( $\pm 30$  min) after administration of BNT112.
- [16] Blood collection before administration of BNT112.
- Blood collection 4 h (±30 min) after administration of BNT112.
- [18] Variable time point; either during screening ≤7 d or at C1D1 before administration of BNT112.
- [19] A sample should be taken at EoT or at Safety FU and only if one has not previously been taken at C8D15.
- At screening for all patients, thereafter only for Arm 1A: thyroid hormones (thyroid stimulating hormone [TSH], free thyroxine [fT4] and triiodothyronine [T3]) will be performed at the times listed and every second cycle after C8 and when clinically indicated at the investigator's discretion.
- On-treatment tumor samples from biopsies or tumor resections done as part of the clinical management of the patient (e.g., palliative surgery) will optionally be provided for additional potential biomarker research.
- [22] Randomization can be performed up to 1 day before C1D1.

CONFIDENTIAL Page 29 of 122

### 1.4. Schedule of Activities: Part 2 Arms 2 and 3

	Scree	ening	Treatment													Follow-	up (FU	)				
1 cycle = 21 days				C1			C2		C	23	C4	C5	C6	C7	C	C8	ЕоТ*	Safety FU **	Effic FU		TIX7	C
Visit	≤28d	≤7d	D1	D8	D15	D1	D8	D15	D1	D15	D1	D1	D1	D1	D1	D15	E01"	D30/ D90	М6	M12	UV	Surgery
Visit window				±1d	±1d	±1d	±1d	±1d	±1d	±3d	±1d	±1d	±1d	±1d	±1d	±3d		+7d	±14d	±14d		
Patient information/ consent 	X																					
Demographic data	X																					
Medical history  and body height	X																					
Body weight	X										X&						X	X				
Physical examination 	X		X	X	X	X	X	X	X		X	X	X	X	X		X	X			$X^{[5]}$	

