# 4. Trial Design

# 4.1. Overall Design

The trial consists of 2 parts: Part 1 (dose titration) and Part 2 (dose expansion). Part 2 consists of four arms: Arms 1A and 1B (mCRPC patients) and Arms 2 and 3 (LPC patients).

Part 1 contains a dose titration for initial safety assessment and identification of the recommended expansion dose range (REDR). It will enroll mCRPC patients to receive BNT112 monotherapy at 3 predefined dose levels (DLs) until a discontinuation-of-treatment criterion is met (Section 7). Part 1 of the trial will employ a modified 3+3+3 design (adapted from Hamberg et al. 2010^13) with up to 9 evaluable patients.

Once the REDR is defined, the trial will commence with Part 2 and enroll approximately 106 patients in four arms (the expansion part, Section 4.2). Part 2 Arms 1A and 1B will enroll patients with mCRPC to receive BNT112 monotherapy or BNT112 in combination with cemiplimab, and Part 2 Arms 2 and 3 will enroll patients with newly diagnosed LPC eligible for treatment with ADT (e.g., goserelin acetate) to receive BNT112 monotherapy or BNT112 in combination with cemiplimab.

Enrollment between Arms 1A and 1B in Part 2 and between Arms 2 and 3 will be randomized 1:1 to avoid enrollment bias.

The treatment in Part 2 Arms 1A and 1B will continue until a discontinuation-of-treatment criterion is met (Section 7). In Part 2 Arms 2 and 3 the treatment will be stopped at Cycle 8 Day 1 (C8D1) or until a discontinuation-of-treatment criterion is met (Section 7).

The safety of BNT112 in doses  $\mu$ g,  $\mu$ g, and  $\mu$ g, and  $\mu$ g will be evaluated based on DLTs during the first treatment cycle (21 days) as well as the overall incidence of BNT112-related or potentially related TEAEs in both parts of the trial. The safety of concomitant administration of cemiplimab will be evaluated based on the overall incidence of cemiplimab-related or potentially related TEAEs in Part 2 Arms 1A and 2 of the trial and will follow the same rules as Part 1, until the SRC reviews and confirms that the combination safety profile is acceptable to continue with the enrollment for the combination arms. The safety will be evaluated by the SRC. For details, please refer to Section 9.6 and the SRC charter.

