Both clinical trial populations were selected and refined together with clinical experts from the field to enable the real-life clinical setting where the benefit for the patients might be the highest. The clinical setting is further justified by several factors recognized as relevant and important for development of cancer vaccines, also listed in the FDA Guidance for Industry "Clinical Considerations for Therapeutic Cancer Vaccines". These include the time to develop an anti-tumor response, which is generally longer for immunotherapies, and the higher chance for a cancer vaccine to show efficacy in lower tumor burden patients and patients with limited prior therapy exposure.

All patients in Part 2 Arms 2 and 3 will receive up to 3 DLs of BNT112 during the C1 intrapatient dose titration based on the REDR defined in Part 1, thereby allowing for a safe combination with cemiplimab. The safety of this combination is further supported by data from the ongoing Lipo-MERIT trial where no differences were seen between RNA-LPX monotherapy and combination with anti-PD-1 or BRAF/MEK (serine/threonine-protein kinase B-Raf/mitogen-activated protein kinase kinase) inhibitors. All combinations in that trial indicate a well-tolerated safety profile of these combinations with Lipo-MERIT vaccine doses ranging from Lipug to Lipug. Safety of the treatment arms with BNT112 and cemiplimab combination will be reviewed and will follow the same rules as Part 1, until the SRC reviews and confirms that the combination safety profile is acceptable. Based on the recommendation from the SRC, the sponsor will decide if enrollment should continue for the combination arms. More details are provided in the SRC charter.

Randomization in a 1:1 ratio between Part 2 Arms 1A and 1B and between Part 2 Arms 2 and 3 is included to avoid enrollment bias.

CONFIDENTIAL Page 50 of 122

Eligibility criteria are based primarily on clinical safety data from the Lipo-MERIT trial as well as standard eligibility criteria for mCRPC and LPC.  Eligibility criteria for the Part 2 Arm 2 (combination with cemiplimab) of the trial are, in addition, based on available safety data for cemiplimab as well as studies with anti-CTLA-4 and with anti-PD-1 treatments. 

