- 2. Patients with a known history or current malignancy other than the inclusion diagnosis. Note: Exceptions are patients with malignancies with a negligible risk of metastasis or death, that have been adequately treated, such as non-invasive basal cell or non-invasive squamous cell skin carcinoma, non-invasive, superficial bladder cancer, and any cancer with a complete response (CR) that lasted more than 2 years may be included.
- 3. Patients who have had a splenectomy.
- 4. Patients who have had major surgery (e.g., requiring general anesthesia) within 4 weeks before screening, or have not fully recovered from surgery, or have a surgery planned during the time of trial participation, except for the radical prostatectomy planned for patients in Part 2 Arms 2 and 3.
- 5. Patients who have a known history of any of the following:
  - a. HIV 1 or 2
  - b. Hepatitis B (carrier or active infection)
  - c. Hepatitis C (unless considered cured 5 years post curative anti-viral therapy)
- 6. Patients with a known allergy, hypersensitivity, or intolerance to BNT112 or its excipients (all patients in Parts 1 and 2), cemiplimab or its excipients (patients in Part 2 Arm 1A, Arm 1B switch-over patients, and Arm 2 only), or to ADT (e.g., goserelin) or excipients thereof (patients in Part 2 Arms 2 and 3 only).
- 7. Patients with any condition for which, in the opinion of the investigator, participation would not be in the best interest of the patient (e.g., compromise the well-being) or that could prevent, limit, or confound the protocol-specified assessments.
- 8. In situations where trial patients are not legally competent to provide consent (e.g., mentally incapacitated), these patients are not allowed to enter the trial.

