## **Prior/Concomitant Therapy**

- 9. Patients who have received or currently receive the following therapy/treatment:
  - a. Chronic systemic immunosuppressive corticosteroid treatment (prednisone >5 mg daily PO or IV, or equivalent) during the trial.

    Note: Replacement therapy (e.g., physiologic corticosteroid replacement therapy for adrenal or pituitary insufficiency) is not considered a form of systemic treatment and is permitted.
  - b. Prior treatment with other immune-modulating agents that was (a) within fewer than 4 weeks (28 days) or 5 half-lives (whichever is longer) prior to the first dose of cemiplimab, or (b) associated with immune-mediated AEs that were Grade ≥1 within 90 days prior to the first dose of cemiplimab, or (c) associated with toxicity that resulted in discontinuation of the immune-modulating agent.

CONFIDENTIAL Page 56 of 122

- c. Prior treatment with other immune-modulating agents for any non-cancer disease within 4 weeks or 5 half-lives of the agent (whichever is longer) before the first dose of IMP.
- d. Prior treatment with live-attenuated vaccines within 4 weeks before the first dose of IMP and during treatment with IMP.
- e. Prior treatment with an investigational drug (including investigational vaccines) within 4 weeks or 5 half-lives of the agent (whichever is longer) before the planned first dose of IMP.
- f. Therapeutic PO or IV antibiotics within 14 days prior to enrollment.

  Note: Patients receiving prophylactic antibiotics (e.g., for prevention of a urinary tract infection or chronic obstructive pulmonary disease) may be enrolled.
- g. Concurrent use of herbal products that may decrease PSA levels (e.g., saw palmetto).

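### Two cemiplimab-related exclusions depend on the allocated arm, so any loss after 1:1 randomisation can fall on the cemiplimab arms alone

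*Protocol*

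**What the plan says.** **Allocation.** Protocol section 4.1: "Enrollment between Arms 1A and 1B in Part 2 and between Arms 2 and 3 will be randomized 1:1 to avoid enrollment bias". Section 4.3 repeats the aim for "Randomization in a 1:1 ratio between Part 2 Arms 1A and 1B and between Part 2 Arms 2 and 3". Footnote [22] to the schedule in section 1.3, and the matching footnote [23] in section 1.4, fix the timing: "Randomization can be performed up to 1 day before C1D1". Both schedules mark the eligibility criteria again on C1D1, before dosing.

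**Exclusion 6** (synopsis and section 5.2) limits its cemiplimab part by arm: "cemiplimab or its excipients (patients in Part 2 Arm 1A, Arm 1B switch-over patients, and Arm 2 only".

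**Exclusion 9b** (synopsis and section 5.2) concerns earlier immune-modulating agents and has three limbs. Limb (a) is a washout: "within fewer than 4 weeks (28 days) or 5 half-lives (whichever is longer) prior to the first dose of cemiplimab". Limb (b) covers prior treatment "associated with immune-mediated AEs that were Grade ≥1 within 90 days prior to the first dose of cemiplimab". Limb (c), toxicity that ended the earlier agent, has no date. The synopsis places 9b under the heading "Exclusion criteria for all patients".

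**Rationale.** Section 4.3 adds that "Eligibility criteria for the Part 2 Arm 2 (combination with cemiplimab) of the trial are, in addition, based on available safety data for cemiplimab".

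**Waivers.** The opening of section 5 and section 8 both rule out waivers or exemptions.

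**Switch-over.** The schedule in section 1.5 for Arm 1B patients who move to cemiplimab has no eligibility row at CemC1.

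**The concern.** In a randomised comparison each patient should be eligible for either arm before the allocation is known. Here the written criteria do not ensure that. A patient with known cemiplimab hypersensitivity, or with a recent immune-mediated event after an earlier agent, can be in or out depending on the arm he draws, and a check after the draw is on the schedule.

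At stake is the comparability of Arm 1A with 1B and of Arm 2 with 3. SAP section 8.1 plans log-rank tests and hazard ratios for these pairs, and the mITT set is the primary efficacy set. Randomisation is the only protection those comparisons have. A secondary problem is that exclusion 6 names switch-over patients, who cannot be identified at entry, while the switch-over schedule gives no point at which to apply it.

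**Working it through.** **1. Same patient, four arms (exclusion 6 or 9b(b), read literally)**

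| Allocated arm | Exclusion 6, cemiplimab part | Exclusion 9b(b) | Result at entry |
|---|---|---|---|
| 1A | applies | dated from C1D1 | ineligible |
| 1B | only on switch-over | no cemiplimab dose at entry | eligible |
| 2 | applies | dated from C1D1 | ineligible |
| 3 | does not apply | no cemiplimab dose | eligible |

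**2. Limbs (a) and (c) of 9b.** In Arms 1A and 2 the first cemiplimab dose falls on C1D1, the day of first IMP. The limb (a) washout is largely repeated, dated from first IMP, in 9c (non-cancer agents, all patients) and in 15c (anti-cancer immunomodulators, mCRPC). So limb (a) creates little difference between arms. Limb (c) creates none. What remains is exclusion 6 and limb (b).

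**3. How a loss could arise.** With waivers barred, an affected patient allocated to Arm 1A or 2 has two paths. If he is not dosed and has no post-baseline assessment, he is outside the mITT set (Protocol 9.3, SAP 7.1). If he is dosed, he may count as an important eligibility deviation and leave the PP set (SAP 7.1 and 7.2). His counterpart in Arm 1B or 3 takes neither path.

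**4. The plan's own figure.** The Simon rule is to stop at 1 or fewer responses in 20 and to reject at 5 or more in 33.

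P(reject | p) = Σ over x from 2 to 20 of P(Bin(20, p) = x) × P(Bin(13, p) ≥ 5 − x)

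- p = 5%: 0.0218, within the stated 2.5%.
- p = 20%: 0.802, matching the stated 80%.

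The formula contains nothing from the other arm and counts evaluable patients only, so this point does not change it.

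**5. Scale, under assumed frequencies.** The documents give no rate. Let q be the share of randomised patients who meet the cemiplimab part of exclusion 6 or 9b(b). Expected number = q × n; chance of at least one = 1 − (1 − q)^n.

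| q (assumed) | n = 20: expected, chance of ≥1 | n = 33: expected, chance of ≥1 |
|---|---|---|
| 1% | 0.2, 18% | 0.3, 28% |
| 3% | 0.6, 46% | 1.0, 63% |
| 5% | 1.0, 64% | 1.7, 82% |
| 10% | 2.0, 88% | 3.3, 97% |

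The 33 is the planned maximum per mCRPC arm. SAP 8.7.6 reports that enrolment there stopped after the interim analysis, so that column is an upper bound.

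**6. Effect on an observed difference.** Suppose there is no true difference, unaffected patients respond at rate p, and affected patients respond at rate r and are lost from one side only. The spurious difference is p − [(1 − q)p + qr] = q(p − r). With p = 20% and r = 0, it is 0.2, 1.0 and 2.0 percentage points for q = 1%, 5% and 10%. With r = 10% it is half of that. One response in 20 patients is 1/20 = 5 points. This illustrates scale on ORR; the effect on a hazard ratio cannot be worked out from the documents.

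**The case against.** The case against has several parts.

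- **Section 4.3 is not a criterion.** A reader might infer from it that Arm 2 has its own eligibility list. It does not: section 5.2 has no Arm 2-only list, and the LPC-specific exclusion covers Arms 2 and 3 together. This stands, so the point rests on exclusions 6 and 9b(b).
- **9b is headed for all patients.** This stands for limb (c), and in practice for limb (a). It does not help limb (b), which has no reference date in a monotherapy arm at entry.
- **Removal is not prescribed.** A reader might infer that the plan removes patients after randomisation. No rule says so, and section 8 requires eligibility to be confirmed from screening, so a careful site could apply exclusion 6 to everyone beforehand. That is a sensible practice, but the wording of exclusion 6 does not ask for it.
- **The rate may be near zero.** This largely stands. LPC patients are treatment-naive, so 5% or 10% has no support there. In mCRPC, earlier PD-1 or PD-L1 treatment is allowed after washout, but limb (b) also needs a qualifying event within 90 days.
- **Safeguards exist.** The ITT set keeps all randomised patients, ITT sensitivity analyses are planned for ORR and conditionally for PFS, and SAP 8.5 tabulates exclusions from each set by arm with reasons. These stand, with one limit: under SAP 8.7.4.1 an untreated patient without a post-baseline response is censored at the start of PFS, so his inclusion in the ITT set adds almost nothing to that comparison.

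**Conclusion.** The point holds in a narrow form. Exclusion 6 in words, and 9b(b) in effect, make eligibility depend on an arm that is unknown until randomisation. With waivers barred, losses from the mITT or PP set can then fall on the cemiplimab side only.

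The likely size is small. Even at an assumed 10%, with every affected patient a non-responder, the spurious ORR difference is 2.0 percentage points, less than one response in an arm of 20. This rests on assumed values of q; the true frequency is unknown and probably low, particularly in LPC.

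A reader might go further and conclude that the primary efficacy result is compromised, or that the paired arms come from materially different populations. The documents do not support either. The primary tests are run per arm against 5%, no formal comparison between arms is planned, and most immune-related exclusions apply to both sides. What is at risk is the exploratory comparison of 1A with 1B and of 2 with 3.

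**What to change.** 1. State in section 5.2 that the cemiplimab part of exclusion 6 and all of 9b are assessed and documented for every Part 2 patient before randomisation, so that each patient is eligible for either arm of his pair. Align the sentence in section 4.3.
2. For entry, date 9b from the first dose of IMP, which every arm has. Keep the first dose of cemiplimab as the reference for Arm 1B switchers; replacing it throughout would leave them without a date.
3. Reconcile exclusion 6, which names switch-over patients, with the section 1.5 schedule, which has no eligibility row at CemC1.
4. Because mCRPC enrolment has stopped, wording changes cannot help entry to Arms 1A and 1B. For those arms, report by arm any patient randomised but not treated because of a cemiplimab-related criterion. The SAP 8.5 table of exclusions can carry this if the reason is recorded specifically.

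The cost is protocol wording, a reconciled schedule and one reporting line. The downside is that a few patients who could have had monotherapy are screened out.

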#### 4.4. Dose and Schedule Rationale

One of the purposes of early phase trials is to determine the optimal dose and schedule for a particular treatment. For classical chemotherapy and targeted agents, the highest tolerated dose will usually be the most effective and is often taken forward in later stage studies. For checkpoint inhibitors, the anti-tumor effect may reach a plateau after which an increased dose confers neither increased toxicity nor improved benefit. In contrast, for cancer vaccines, a maximum tolerated dose (MTD) is rarely reached, the effective range may be very broad, and there usually is some minimum threshold that elicits an immune response. 9 The impact of antigen dose on immune response is controversial. A trial evaluating the immunologic response to high, medium, and low doses of a human epidermal growth factor receptor 2 (HER2)/neu intracellular domain protein-based vaccine showed differences in the kinetics of the expansion of an antigen-specific T cell response, but no difference in the overall magnitude of the T cell response, antibody response or avidity. 12 There is evidence that different doses of peptide vaccines selectively stimulate expansion of T cells with different levels of avidity and cytotoxicity.  Moreover, the impact of different vaccine administration schedules on immune response has not been thoroughly explored. Most studies do not explore different vaccine dosing schedules and, therefore, the ideal vaccine dosing schedule has not been identified. The dose titration part as well as the expansion cohorts will investigate potential large differences in immune response and preliminary anti-tumor efficacy of DLs below the MTD/maximum administered dose alone or in combination with ADT (e.g., goserelin acetate) with or without cemiplimab in order to inform dose and schedule in pivotal studies.

**BNT112:** The proposed starting dose and dosing schedule of BNT112 as a single agent is based primarily on the safety, immunogenicity, preliminary efficacy, and generated in the ongoing clinical trials with the sponsor's RNA-LPX as well as on an integrated assessment of the proposed MoA (i.e., generation of a T cell response to a tumor shared antigen), efficacy in murine tumor models, and *in vivo* safety in the GLP toxicity studies conducted in mice.

Based on preliminary analysis of safety, efficacy and immunogenicity data of the Lipo-MERIT trial as well as the other ongoing Phase 1 clinical trials, a dose range of CCI, and CCI µg was proposed to be tested in the Part 1 dose titration part of this trial.

The step-up dose titration follows the approach implemented in the ongoing clinical trials with RNA cancer vaccine IMPs and allows for optimal dose management on an individual basis, and accounts for inter- and intra-individual variability of the immune system. Step-up dosing may offer advantages over flat dosing, including the potential mitigation of a hypothetical first dose phenomenon (i.e., allowing the patient to acclimate to gradually increasing doses of BNT112) with the lower starting dose acting as a "lead-in" dose potentially mitigating immune system activation-related AEs. This approach was confirmed in the previous and ongoing sponsor trials with RNA-encoded cancer vaccines. The dosing schedule proposed in this trial is based primarily on the Lipo-MERIT trial (6 weekly vaccinations followed by 2 bi-weekly vaccinations followed by continuous treatment with the maximum individually tolerated dose given every 28 days for

CONFIDENTIAL Page 51 of 122

patients without PD). The dosing schedule in the proposed prostate cancer trial includes the intensified weekly dosing in C1 and C2 followed by the treatment with the maximum individually tolerated dose every 21 days. The schedule also fits the dosing schedule for cemiplimab (every 21 days) and both are easily incorporated in the standard dosing of the ADT (e.g., goserelin acetate is given Q12W).

Part 1 (dose titration) of the PRO-MERIT trial has been performed in the UK and Hungary and enrollment has been completed with 9 patients dosed. The SRC reviewed the available safety data for patients in Part 1 on 17 MAY 2021. The safety profile observed indicates that BNT112 a tolerable drug product with a manageable safety profile at the defined dose range µg) using the intra-patient step-up dose titration scheme. Observed AEs considered related to the IMP (including pyrexia, flu-like symptoms, hypertension, nausea, chills or headache), are in line with the innate immune activation by RNA-LPX, are transient in nature and manageable by analgesics, antipyretics or fluids at recommended and usual doses. The recommendation was to continue to Part 2 at the selected REDR ( to QCI µg) using the intra-patient step-up dose titration scheme. The annual review of safety data for the IB update occurred on 20 MAY 2021 (data extraction date) and included safety data from patients in Part 1 as well as Part 2. Neither the safety profile nor the benefit-risk assessment were changed.

**Cemiplimab** is given at a dose of mg as an IV infusion over 30 minutes every 3 weeks.

Goserelin acetate is administered at a dose of 10.8 mg as an SC injection into the anterior abdominal wall Q12W, according to the current SmPC (e.g., Zoladex® LA 10.8 mg implant). In order to facilitate interpretation of toxicities with suspected relationship to the IMP, goserelin acetate is to be administered anytime within 7 days prior to the start of BNT112 treatment. In case another ADT is used, it is to be administered in line with the current prescribing information valid in a given country.

